6.3.2.1. Overview of AEs

An overall summary of unsolicited AEs up to 7 days after each injection, between 8 to 21 days after each injection, and up to 21 days after each injection will be provided, for the number and percentage of participants, along with the number of events, by treatment group who experience at least one of the categories:

- Any unsolicited AEs
- Any serious AEs
- Any fatal AEs
- Any unsolicited medically-attended AEs

- Any unsolicited AEs leading to discontinuation from study vaccine
- Any unsolicited AEs leading to study discontinuation
- Any unsolicited severe AEs
- Any unsolicited non-serious AEs (no SAE)
- Any unsolicited non-serious severe AEs (no SAE)
- Any unsolicited non-serious AEs (regardless of SAE)
- Any unsolicited non-serious severe AEs (regardless of SAE)
- Any unsolicited AESI

Note: Severe AEs include both unsolicited severe AEs and ≥Grade 3 solicited ARs that meet SAE criteria or last beyond 7 days after each injection.

Summary tables will also be provided to include number and percentage of participants with unsolicited AEs that are treatment-related in each of the above categories.

Additionally, the overall summary for the categories of SAEs, MAAEs, AESIs, and AEs leading to study discontinuation will be provided for these AEs throughout the study.

Separate listings containing individual participant AE data throughout the study for AEs, treatment-related AEs, serious AEs, serious treatment-related AEs, medically-attended AEs, treatment-related medically-attended AEs, AEs leading to discontinuation from study vaccine, AEs leading to study discontinuation, severe AEs, treatment-related severe AEs, AESIs, and fatal AEs will be provided.

Listing of deaths, including cause of death, will be provided.

6.3.2.2. AEs by System Organ Class and Preferred Term

The following summary tables of unsolicited AEs up to 21 days after each injection will be provided by SOC and PT using frequency counts and percentages (i.e., number and percentage of participants with an event):

- All unsolicited AEs
- All unsolicited AEs that are treatment-related
- All serious AEs
- All serious AEs that are treatment-related
- All unsolicited non-serious AEs (regardless of SAE)
- All unsolicited non-serious severe AEs (regardless of SAE)

- All unsolicited medically-attended AEs
- All unsolicited medically-attended AEs that are treatment-related
- All unsolicited AEs leading to discontinuation from study vaccine
- All unsolicited AEs leading to study discontinuation
- All unsolicited severe AEs
- All unsolicited severe AEs that are treatment-related
- All unsolicited treatment emergent AESI

Note: Severe AEs include both unsolicited severe AEs and ≥Grade 3 solicited ARs that meet SAE criteria or last beyond 7 days after each injection.

Summary tables by SOC and PT will also be provided for number and percentage of participants with unsolicited AEs up to 7 days after each injection, and between 8 to 21 days after each injection.

Additionally, summary tables of SAEs, treatment-related SAEs, MAAEs, treatment-related MAAEs, AEs leading to study discontinuation, and AESIs will be also provided by SOC and PT considering all events reported throughout the study.

6.3.2.3. **AEs by Preferred Term**

A summary table for all unsolicited AEs up to 21 days after each injection will be provided by PT in descending order of frequency in the "D1: Fluzone HD+mRNA-1345 (μg) and D22: placebo" group.

6.3.2.4. AEs by Severity

The following summary tables of AEs up to 21 days after each injection will be provided by the severity, SOC and PT using frequency counts and percentages:

- All unsolicited AEs
- All unsolicited AEs that are treatment-related

Summary tables of unsolicited AEs up to 21 days after each injection with occurrence in \geq 1% of participants in any treatment group based on preferred term will be also provided by severity, SOC and PT.

6.3.2.5. **AEs by SMQ**

The number of events and number of participants reported occurrence of selected AEs of clinical interests identified by SMQs up to 7 days after each injection, up to 21 days after each injection, and throughout the study will be summarized by SMQ, subordinate SMQ, and PT. Two sets of

summary tables will be provided, one will be based on combined broad and narrow scope of SMQ, the other will be based on narrow scope. SMQ and subordinate SMQ within each SMQ will be displayed in alphabetic order. PT will be displayed in descending order of number of participants in "D1: Fluzone HD+mRNA-1345 (µg) and D22: placebo" group and then alphabetically within subordinate SMQ or SMQ if no subordinate SMQ. Detail information for the selected SMQ is presented in Appendix H Table 7 and Table 8.

Selected AEs of clinical interests identified by SMQs up to 21 days after each injection and throughout the study will be provided in listings.

6.3.2.6. AEs by System Organ Class, High Level Group Term, and Preferred Term

Certain AEs, as indicated in Appendix I, will also be summarized by SOC, HLGT, and PT for each treatment group and presented by three time periods: up to 7 days after each injection, up to 21 days after each injection, and throughout the study.

6.3.2.7. Independent Cardiac Event Adjudication Committee (CEAC)

An independent CEAC of medically qualified personnel, including cardiologists, will review suspected cases of myocarditis and pericarditis to determine if they meet CDC criteria of "probable" or "confirmed" events, and to assess severity (see more details in Section 10.1.6.2 of the protocol) and provide the assessment to the Sponsor. The CEAC members will be blinded to study treatment. Details regarding the CEAC composition, responsibilities, procedures, and frequency of data review can be found in the CEAC charter.

A summary table will be provided based on the data adjudicated by the CEAC, as the primary analysis of cardiac events.

Cardiac events adjudicated by the CEAC will be provided in a listing.

6.3.2.8. Subgroup Analysis of AEs

The overview of AEs, AEs by SOC/PT, AEs by Severity, unsolicited treatment-related AEs by SOC/PT and serious AEs by SOC/PT may be provided for the following subgroup:

- Age group (65 to <75 years, \ge 75 years)
- Sex (Male, Female)

- Race (White, Black, Asian, Other [including American Indian or Alaska Native, Native Hawaiian or other Pacific Islander and other races])
- Ethnicity (Hispanic or Latino, Not Hispanic or Latino)

These summaries may be provided for additional subgroups of selected baseline characteristics. If the number of participants in certain subgroups are too small, it may be combined with the other subgroups for the subgroup analyses.

6.3.3. Vital Sign Measurements

Vital signs will only be collected at Screening and on the day of injection (Day 1 and Day 22), once before and at least 30 minutes after each injection. Vital signs will be collected at other study visits only in conjunction with a symptom-directed physical examination.

Vital sign measurements, including systolic and diastolic blood pressures, pulse rate, respiratory rate and body temperature will be presented in a data listing. The values meeting the toxicity grading criteria (DHHS 2007) will be flagged in the data listing.

For each injection (Day 1 or Day 22), the observed pre-injection and post-injection values and change from pre-injection to post-injection will be summarized by treatment group. Shift from pre-injection to post-injection in the toxicity grades for each injection will also be summarized by treatment group.

The abnormalities meeting the toxicity grading criteria (Grade 2 or higher) in any vital sign measurement will be listed separately. If a participant has a vital sign result with Grade 2 or higher abnormality at any post injection visit, then all results of that specific vital sign for that participant will be presented in the listing.

6.4. Immunogenicity Analysis

The analyses of immunogenicity will be using the PP Set, by treatment group. The supportive analyses of immunogenicity especially for primary immune response will be conducted using the FAS based on Appendix G. If the number of participants in the FAS and PP Set differ (defined as the difference divided by the total number of participants in the PP Set) by more than 10%, additional supportive analyses of non-primary immunogenicity may be conducted using the FAS.

The GMT, GMC, and GM level will be calculated using the following formula:

$$10^{\left\{\frac{1}{n}\sum_{i=1}^{n}\log_{10}(y_{it})\right\}}$$

where $y_{1t}, y_{2t}, \dots, y_{nt}$ are *n* observed immunogenicity titers or levels for participants $i=1, 2, \dots, n$ at time point t.

The GMFR measures the changes in immunogenicity titers or levels from baseline within participants. The GMFR will be calculated using the following formula:

$$10^{\left\{\frac{1}{n}\sum_{i=1}^{n}\log_{10}\left(\frac{y_{it}}{y_{i0}}\right)\right\}} = 10^{\left\{\frac{1}{n}\sum_{i=1}^{n}[\log_{10}(y_{it}) - \log_{10}(y_{i0})]\right\}}$$

where $y_{1t}, y_{2t}, \dots, y_{nt}$ are observed immunogenicity titers or levels for participants i's at time point t. and $y_{10}, y_{20}, \dots, y_{n0}$ are immunogenicity titers or levels for participants i's at time point 0 (baseline).

6.4.1. Immunogenicity Assessments

Immunogenicity assessments will include the following:

- Serum RSV-A and RSV-B nAbs as measured by microneutralization assay
- Serum anti-HA Abs for each influenza strain (A/H1N1, A/H3N2, B/Yamagata, B/Victoria) as measured by HAI assay

RSV binding antibody levels may be presented as appropriate.

6.4.2. Analysis of the Primary Immunogenicity Endpoints

The coprimary endpoints will be analyzed on the PP Set in order to estimate Estimands 1a-2a (refer to Appendix G, Table 5). In addition, this will be supported by estimation of a treatment policy Estimand (Estimands 1b-2b) on the FAS Set.

6.4.2.1. Primary Analysis Approach

The coprimary endpoints include the following:

- GMT of serum RSV-A and RSV-B nAbs at Day 22 (Arm 1) and Day 43 (Arm 2)
- GMT of serum influenza anti-HA Abs as measured by HAI assay at Day 22

The statistical analyses are:

• For each coprimary endpoint, the GMR will be estimated using an analysis of covariance (ANVOVA) model on the log-transformed titers, with the treatment group and log-transformed baseline titers as the fixed covariate, adjusted for stratified age group used for randomization. The geometric least square mean (GLSM) for each treatment group and its corresponding 95% CI in a log-transformed scale will be estimated from the model and back-transformed to obtain these estimates in the original scale as an estimate of the GMT and its 95% CI. The GMR estimated by the ratio of the GLSMs and the corresponding 2-sided 95% CI will be provided to assess the treatment difference in the immune response between the 2 treatment groups. For each coprimary endpoint, the

noninferiority of the GMT will be demonstrated if the LB of the 95% CI of the GMR is >0.667 based on a noninferiority margin of 1.5.

• Additionally, GMT of RSV-A nAb, RSV-B nAb, and influenza anti-HA Abs for each influenza strain with corresponding 95% CI will be provided at each visit (as applicable) by treatment group. The 95% CIs will be calculated based on the t-distribution of the log-transformed values and then back transformed to the original scale for presentation. The following descriptive statistics will also be provided at each visit: the number of participants (n), median, minimum and maximum. GMT with 95% CI will be plotted at each visit (as applicable) by treatment group.

The study is considered to meet the primary immunogenicity objective if the noninferiority of the immune response to mRNA-1345 coadministered with Fluzone HD is met based on all the coprimary endpoints.

The above analysis corresponds to the Primary Immune Estimands 1a-2a as described in Appendix G, Table 5.

6.4.2.2. Sensitivity Analysis

Analyses of the primary endpoints will be performed based on the FAS, using the same method and same definition as described in Section 6.4.2.1.

This sensitivity analysis corresponds to the Supportive Immune Estimands 1b-2b as described in Appendix G, Table 5.

6.4.3. Analysis of the Secondary Immunogenicity Endpoints

The secondary endpoints include the following:

- SRR in RSV-A and RSV-B nAbs at Day 22 (Arm 1) or Day 43 (Arm 2)
- GMFR of RSV-A and RSV-B nAbs at Day 22 (Arm 1) or Day 43 (Arm 2) compared to baseline (Day 1 for Arm 1 or Day 22 for Arm 2)
- Proportion of participants with ≥2-fold increase in RSV-A and RSV-B nAbs at Day 22 (Arm 1) or Day 43 (Arm 2) compared to baseline (Day 1 for Arm 1 or Day 22 for Arm 2)
- SCR in influenza anti-HA Abs for each influenza strain at Day 22
- GMFR of influenza anti-HA Abs for each influenza strain at Day 22 compared to baseline (Day 1)

The statistical analyses are:

• SRR in RSV-A and RSV-B nAbs at Day 22 (Arm 1) or Day 43 (Arm 2) will be provided with 2-sided 95% CIs by treatment group using the Clopper-Pearson method. The SRR

difference between the two treatment groups will be provided with 2-sided 95% CIs using the Miettinen-Nurminen's method. For each RSV subtype, the noninferiority of the SRR will be demonstrated if the LB of the 95% CI of the SRR difference is >-10% based on the noninferiority margin of 10%.

- SCR in influenza anti-HA Abs for each influenza strain at Day 22 will be provided with 2-sided 95% CIs by treatment group using the Clopper-Pearson method. The SCR difference between the two treatment groups will be provided with 2-sided 95% CIs using the Miettinen-Nurminen's method. For each influenza strain, the noninferiority of the SCR will be demonstrated if the LB of the 95% CI of the SCR difference is >-10% based on the noninferiority margin of 10%.
- GMFR of RSV-A and RSV-B nAbs at Day 22 (Arm 1) or Day 43 (Arm 2) compared to baseline (Day 1 for Arm 1 or Day 22 for Arm 2), and GMFR of influenza anti-HA Abs at Day 22 compared to baseline (Day 1) will be provided with corresponding 95% CI by treatment group. The 95% CIs will be calculated based on the t-distribution of the difference in the log-transformed values (postbaseline time point baseline) and then back transformed to the original scale for presentation. GMFR with 95% CI will be plotted by treatment group.
- Proportion of participants with ≥2-fold increases in RSV-A and RSV-B nAbs at Day 22
 (Arm 1) and Day 43 (Arm 2) compared to baseline (Day 1 for Arm 1 and Day 22 for Arm
 2) will be provided with 2-sided 95% CIs by treatment group using the Clopper-Pearson method.

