9.5.1. Immunogenicity Analyses

The primary analysis population for immunogenicity will be the PP Set, unless otherwise specified. If the number of participants in the FAS and PP Set differs (defined as the difference divided by the total number of participants in the PP Set) by more than 10%, supportive analyses of immunogenicity may be conducted using the FAS.

The coprimary endpoints include the GMT of RSV-A/RSV-B nAb titers at Day 22 (Arm 1) and Day 43 (Arm 2) and GMT of anti-HA Ab titers at Day 22 for each influenza strain. For each coprimary endpoint regarding GMT, the GMR will be estimated using an analysis of covariance model on the log-transformed titers, with the treatment group and log-transformed baseline titers as a fixed covariate, adjusted for stratified age group used for randomization. The GLSM and its corresponding 95% CI in a log-transformed scale estimated from the model will be back-transformed to obtain these estimates in the original scale as an estimate of the GMT and its 95% CI. The GMR, estimated by the ratio of the GLSM and the corresponding 2-sided 95% CI, will be provided to assess the treatment difference. The corresponding 2-sided 95% CI of the GMR will be provided to assess the difference in the immune response between the 2 treatment groups. For each coprimary endpoint regarding GMT, the noninferiority of the GMT will be demonstrated if the LB of the 95% CI of the GMR is >0.667.

The SRR of RSV-A/RSV-B nAbs is defined as proportion of participants with postvaccination titers $\ge 4 \times \text{LLOQ}$ if baseline is $\le \text{LLOQ}$ or a ≥ 4 -fold increase from baseline if baseline is $\ge \text{LLOQ}$. The SCR of an influenza strain is defined as proportion of participants with a postvaccination

titer \ge 1:40 if baseline is \le 1:10 or a \ge 4-fold rise in postvaccination HAI Ab titer if baseline is \ge 1:10.

The number and percentage of participants with SRR at Day 22 (Arm 1) and Day 43 (Arm 2) or SCR at Day 22 will be provided with 2-sided 95% CI using the Clopper-Pearson method. For secondary endpoints regarding SRR and SCR, the Miettinen-Nurminen's method will be used to calculate the 95% CI for the difference in the SRR or SCR at corresponding timepoint between the treatment groups. For each strain, the noninferiority of SRR or SCR will be considered demonstrated if the LB of the 95% CI of the SRR or SCR difference is >-10% based on a noninferiority margin of 10%.

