4.3. Sample Size and Power

The study will plan to randomize approximately 1900 participants in a 1:1 ratio, with approximately 950 participants receiving Fluzone HD + mRNA-1345 followed by placebo (Arm 1) and 950 participants receiving Fluzone HD + placebo followed by mRNA-1345 (Arm 2).

With approximately 950 participants in each group, the study has approximately 95% probability to observe at least 1 participant with an AE at a true 0.3% AE rate in that group.

Assuming approximately 10% of participants are ineligible to be included in the PP Set, 855 participants will be included in each group. There is at least 98.5% power to demonstrate the noninferiority of the immune response to RSV-A and RSV-B, as measured by GMT of RSV-A and RSV-B nAb at Day 22 (Arm 1) or Day 43 (Arm 2) in participants receiving mRNA-1345 coadministered with Fluzone HD compared with that in mRNA-1345 sequentially administered with Fluzone HD, at a 2-sided alpha of 0.05, assuming a noninferiority margin of 1.5 and an underlying GMR of 0.9. The standard deviation of the natural log-transformed level is assumed to be 1.5.

The global power considered adequate to meet the primary objectives and evaluate the immune responses to RSV-A, RSV-B, and influenza is at least 91.3%. Sample size justification for the coprimary endpoints is shown in Table 2.

Table 2: Sample Size Justification

Coprimary Endpoint	Number of Evaluable Participants (with 10% Ineligible for the PP Set)	α	Standard Deviation	GMR Assumption	NI Margin	Power
mRNA-1345 Noni	nferiority (2-sided test)					
RSV-A GMT						
Day 22 (Arm 1)	855	0.05	1.5	GMR=0.9	1.5	98.5%
versus						
Day 43 (Arm 2)						
RSV-B GMT			05 1.5	GMR=0.9	1.5	98.5%
Day 22 (Arm 1)	855					
versus						
Day 43 (Arm 2)						
Fluzone HD Nonii	nferiority (2-sided test) for	Each I	nfluenza Str	ain		
GMT	855	0.05	1.5	GMR=0.9	1.5	98.5%
Day 22 (Arm 1)						
versus		0.03	1.5			
Day 22 (Arm 2)						
Overall power to show noninferiority on both mRNA-1345 and Fluzone HD					91.3%	

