4.4. Randomization

The randomization will be in a blinded manner using a centralized Interactive Response Technology (IRT) system, in accordance with pre-generated randomization schedules.

The study will enroll approximately 1900 medically stable adults ≥65 years of age. Participants will be randomized with a ratio of 1:1 to receive either 1) Fluzone HD+mRNA-1345 μg on Day 1 followed by placebo (0.9% sodium chloride) on Day 22 (Arm 1); or 2) Fluzone HD+placebo (0.9% sodium chloride) on Day 1 followed by mRNA-1345 μg on Day 22 (Arm 2). Randomization will be stratified by age (65 to <75 years and ≥75 years [approximately 10%]).

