6.5. Multiplicity Adjustment

A sequential/hierarchical testing procedure will be used to control the overall Type 1 error rate at 0.05 (2-sided) over the primary endpoints, and secondary endpoints.

The coprimary endpoints will be tested at the planned primary analysis at a 2-sided Type 1 error rate of 0.05. The success criteria of all 6 coprimary endpoints need to be met in order to declare the study a success to achieve noninferiority of coadministration.

The secondary endpoints on SRR and SCR will only be tested at the primary analysis at a 2-sided Type 1 error rate of 0.05 when all coprimary endpoints have achieved statistical significance. The secondary endpoints will be tested sequentially in the following order: 1) SCR of influenza anti-HA Abs for each influenza strain, 2) SRR of RSV-A nAbs and 3) SRR of RSV-B nAbs.

No further testing will be performed once the sequence/hierarch breaks, that is, further testing stops as soon as an endpoint in the sequence fails to meet success criterion of noninferiority. Analyses of remaining other secondary immune endpoints are not controlled for multiplicity.

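### The six alpha-controlled SRR and SCR noninferiority tests (H7 to H12) ignore the randomisation age stratum; a stratified Miettinen-Nurminen interval would be a small, nearly free improvement

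*SAP*

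**What the plan says.** - **Tested interval.** SAP 6.4.3: "The SCR difference between the two treatment groups will be provided with 2-sided 95% CIs using the Miettinen-Nurminen's method". The SRR sentence there has the same form. Protocol 9.5.1 agrees: "the Miettinen-Nurminen's method will be used to calculate the 95% CI for the difference in the SRR or SCR at corresponding timepoint". No strata, weights or age adjustment appear in either place.
- **Success rule.** Noninferiority is met when "the LB of the 95% CI of the SCR difference is >-10% based on the noninferiority margin of 10" per cent. The SRR rule is the same.
- **Status of the tests.** SAP 6.5: "The secondary endpoints on SRR and SCR will only be tested at the primary analysis at a 2-sided Type 1 error rate of 0.05", once all six coprimary endpoints have succeeded. The order is "1) SCR of influenza anti-HA Abs for each influenza strain, 2) SRR of RSV-A nAbs and 3) SRR of RSV-B nAbs", and testing stops at the first failure. That makes four SCR and two SRR tests.
- **Randomisation.** SAP 4.4: "Randomization will be stratified by age (65 to <75 years and ≥75 years [approximately 10" per cent, the last figure being the share expected in the older stratum.
- **Coprimary model.** The ANCOVA in SAP 6.4.2.1 is "adjusted for stratified age group used for randomization" and also includes the log baseline titre.
- **Age elsewhere.** Protocol 9.5.1 promises descriptive statistics by age group. SAP 6.4.5 makes age subgroup analyses optional. Neither adjusts the interval that decides H7 to H12.

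**The concern.** The design balances the arms on age, and the coprimary analysis uses that balance, but the secondary noninferiority tests do not. If response differs by age, a pooled interval counts the between-stratum spread as noise and comes out slightly too wide for the design. The tests are also run on the PP Set, which is formed after randomisation. If exclusions fall unevenly by age across arms, the crude difference carries that imbalance, whereas the GMT model would adjust for it.

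At stake are six claims inside the controlled hierarchy. The coprimary tests, the sample size and the stated power are not affected.

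**Working it through.** **Inputs from the documents.** 950 randomised per arm, 855 evaluable ("Assuming approximately 10% of participants are ineligible to be included in the PP Set, 855 participants will be included in each group"), 1:1 allocation, about 10% aged ≥75, margin −10 points, two-sided 0.05.

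**Assumed.** The documents give no SRR or SCR rates, so every rate below is an assumption, written younger/older and equal in the two arms unless stated.

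**1. The plan's own figures.** 950 × 0.9 = 855. Coprimary power = Φ[(ln 1.5 + ln 0.9) / (1.5 × √(2/855)) − 1.96] = Φ(0.3001/0.07255 − 1.96) = Φ(2.18) = 98.5%, as stated. For six endpoints, 0.985⁶ = 91.3%, also as stated. No power is given for SRR or SCR, so there is no secondary figure to reproduce.

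**2. Variance.** Let p = 0.9p₁ + 0.1p₂. The pooled variance is p(1−p). The stratified variance is 0.9p₁(1−p₁) + 0.1p₂(1−p₂). The half-width is 1.96 × √(2v/855).

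| Rates | Pooled v | Stratified v | Reduction | Half-width (points) |
|---|---|---|---|---|
| 50%/40% | 0.2499 | 0.2490 | 0.36% | 4.74 to 4.73 |
| 50%/30% | 0.2496 | 0.2460 | 1.44% | 4.74 to 4.70 |
| 70%/40% | 0.2211 | 0.2130 | 3.66% | 4.46 to 4.37 |

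The reduction equals 0.09 × gap² / [p(1−p)], so it also grows as the pooled rate moves away from 50%. At 80%/50% it is 0.0081/0.1771 = 4.6%.

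**3. Miettinen-Nurminen lower bounds.** Expected counts with 770 younger and 85 older per arm, stratum weights n₁n₂/(n₁+n₂):

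| Rates | Unstratified | Stratified | Gain (points) |
|---|---|---|---|
| 50%/40% | −4.73% | −4.73% | 0.007 |
| 50%/30% | −4.73% | −4.70% | 0.033 |
| 70%/50% | −4.42% | −4.39% | 0.035 |
| 70%/40% | −4.46% | −4.38% | 0.080 |
| 80%/50% | −3.99% | −3.90% | 0.089 |

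**4. Type 1 error and power by simulation, balanced strata.** With 20,000 trials per case at 50%/40%, 50%/30% and 70%/50%:

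- One-sided error at a true difference of −10 points is 2.3% to 2.5% unstratified and 2.4% to 2.6% stratified.
- Power at a true difference of −3 points is 83.8% against 83.8%, 83.2% against 83.2%, and 86.9% against 87.2%. The gain is 0 to 0.3 points.

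Those cases stop at a 20-point age gap. A further run of 400,000 trials at 70%/40% gave error of 2.4% against 2.6% (2.55% before rounding) and power of 86.8% against 87.5%, a gain of about 0.7 points.

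**5. Imbalance from PP exclusions.** About 0.10 × 950 = 95 older participants are randomised per arm, and a 10% loss leaves about 85. The most that exclusions can retain is 95 of 855 (11.1%). Set against 85 of 855 (9.9%) in the other arm, the crude difference shifts by (95 − 85)/855 × gap. That is 0.12 points at a 10-point gap, 0.23 at 20 and 0.35 at 30, in either direction. The stratified estimate does not shift.

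**The case against.** The strongest reply is that this is a preference. The unstratified interval is valid under stratified randomisation. SAP 4.2 defines each tested quantity as one group's rate minus the other's, which the crude interval addresses directly. That stands in full. Stratifying would not change the target much, however: with balanced strata the weights are 385 and 42.5, the same 90/10 split as the sample, so the point estimate is the same.

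Consistency with the coprimary model is a weak argument taken alone. The ANCOVA also adjusts for baseline titre, which a stratified interval would not, and no section promises one adjustment set for all endpoints.

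The documents never call the interval unstratified. That is the plain reading of a method named without strata. If a stratified version was meant, its weights are missing and the SAP needs the same sentence.

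A reader might go further in three ways that the documents do not support:

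- **That Type 1 error control is broken.** The simulated error of the planned test is at or just below 2.5% one-sided.
- **That the stopping rule makes this decisive.** The rule is real, but the lower bound moves by less than 0.1 point in every balanced case in step 3, against a 10-point margin.
- **That exclusions could leave, say, 12% against 10% aged ≥75, a 0.4-point shift at a 20-point gap.** 12% of 855 is about 103 people, more than the 95 randomised at a 10% share. Even the 0.23-point case needs one arm to exclude no older participant. The documents give no evidence that exclusions will differ by age and arm.

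**Conclusion.** The point holds as a minor improvement, not as an error. H7 to H12 are analysed without the stratum that was used to randomise and that the coprimary model adjusts for. The planned interval is valid and marginally conservative.

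The variance saving is 0.4% to 3.7% for the three rate pairs in step 2, with a lower-bound gain under 0.1 point. The power gain is 0 to 0.3 points at 10- to 20-point gaps and about 0.7 at 30. Protection against an age imbalance in the PP Set is worth about 0.2 points at a 20-point gap.

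All of this rests on assumed rates and on an older share near 10%. With no age gap in response, the gain is nil.

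**What to change.** Before unblinding, state in SAP 6.4.3 that the SRR and SCR differences use the stratified Miettinen-Nurminen method, by the randomised age stratum (the one used in the ANCOVA), with Mantel-Haenszel weights. Keep the unstratified interval as a sensitivity analysis.

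The cost is SAP wording and one program option, with no new data. One check is needed. Protocol 9.5.1 names the method, and the opening of protocol Section 9 says that changes to methods for secondary hypotheses, made after study start and before unblinding, lead to a protocol amendment. SAP Section 1 lets the SAP prevail where methods differ, and describes its own modifications as not principal in nature. The sponsor should decide which provision applies, align protocol 9.5.1 if needed, and list the change in SAP Section 7. If the unstratified interval is kept, one sentence saying so, with the stratified interval as the sensitivity analysis, would be enough.
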